6.2.6 Expectedness

If the adverse event is judged to be related to the device, the investigator will make an assessment of expectedness based on knowledge of the reaction and any relevant product information as documented in the IFU and current protocol. The event will be classed as either;

- Expected the reaction is consistent with the effects of the device listed in the IFU and protocol;
- Unexpected the reaction is not consistent with the effects listed in the IFU and protocol.

The table below presents the potential expected adverse device effects following the placement of TN-SM and insertion of dental implants.

Table 3: List of expected ADEs following the placement of TN-SM and insertion of dental implants

Biological complications						
Nature of effect Severity (mild, moderate, severe) F (v pr						
Peri-implant mucositis						
Bleeding (BOP Bleeding On Probing)	Mild	Probable				
Bruising	Mild	Frequent				
Delayed healing of the gum	Mild	Rare				
Inflammatory papillary hyperplasia	Mild	Probable				

Gingival/mucosal hyperplasia	Mild	Probable
Pain	Mild to Moderate	Probable
Recession/dehiscence of the gum	Moderate	Rare
Redness	Mild	Probable
Suppuration	Moderate	Rare
Swelling/gingival inflammation	Mild	Probable
Peri-implantitis		•
Bleeding (BOP Bleeding On Probing)	Mild	Probable
Bone loss around implant	Moderate	Probable
Bruising	Mild	Frequent
Infection at implant site without suppuration (not recurrent)	Mild to Moderate	Rare
Infection at implant site with suppuration (not recurrent)	Moderate	Rare
Recurrent infection at implant site without suppuration	Moderate to Severe	Rare
Recurrent infection at implant site with suppuration	Moderate to Severe	Rare
Systemic infection	Severe	very rare
Pain	Mild to Moderate	Probable
Swelling	Mild	Probable
Bone integration deficiency		
Early loss/exfoliation (within 2 weeks after surgery)	Moderate	Rare
Late loss/exfoliation (after prosthetic restoration)	Moderate	Rare
Implant mobility (tactile horizontal or vertical)	Moderate	Rare to Probable
Crestal ridge height bone loss	Mild to Moderate	Rare
Fibrous tissue around implant	Moderate	Rare
Ectopic bone growth	Moderate	very rare
Non-plaque related		
Chronic pain in connection with the dental implant	mild to moderate	Rare
Foreign body sensation	Mild	Rare
Material allergy	Moderate	very rare
Oro-sinus or oro-nasal intrusion/fistula	Severe	Rare

Permanent paresthesia, dysesthesia	Severe	very rare
Temporary or permanent paresthesia in the jaw	Severe	Rare
Mechanical complications		
Loosening of dental implant	Mild	Probable
Loss of dental implant	Mild	Probable
Migration of TN-SM	Mild	Probable
Fracture of TN-SN	Moderate	Rare
Other complications		
Aspiration of implant	Severe	Very Rare
Swallowing of implant	Severe	Very Rare
Aesthetic problem	Mild	Probable
Aspiration of component(s) (other than implant)	Severe	Rare
Jaw, bone fracture	moderate to severe	very rare
Phonetic difficulties	mild to moderate	Rare
Swallowing of component(s) (other than implant)	Severe	very rare
Hypersensitivity (adjacent teeth)	Mild	Rare

6.3 Procedure for Reporting Adverse Events

Adverse event reporting will begin at the time a subject provides written informed consent and ends after a subject withdraws from the study or completes the final study visit. For screen failure subjects, any AEs, ADEs, and DDs that occur from the time of informed consent up until the date on which the subject is deemed ineligible for the study will be recorded on a case report form. Only one AE/SAE case report form should be completed per event. To ensure patient confidentiality, the following reports will include the patient number only.

6.3.1 AE Reporting

In the occurrence of an AE, data should be entered into the AE case report form in the EDC system within five working days of awareness of the event. Safety reporting to the IRB should occur according to the requirements of the local IRB.

6.3.2 SAE Reporting

In the occurrence of a serious adverse event (SAE), expedited reporting requirements are followed.

The SAE case report form should be completed in the EDC within 24 hours of awareness of the event. RevBio will receive an automated notification generated by the EDC system. Safety reporting to the IRB should occur according to the requirements of the local IRB. It is recognized that in many cases SAEs will be treated in a medical rather than a dental environment and the investigator may not have immediate knowledge of the event. The investigator should report an SAE as soon as he/she has knowledge of the event within the above time frame irrespective of when the actual event occurred.

6.3.3 DD Reporting

The Investigator should report all device deficiencies to RevBio by submitting a description to the following email address: [contact]

If appropriate, the product shall be returned in appropriate packaging by courier (trackable method) directly to:

Regulatory Affairs RevBio [name]

When a device deficiency leads to a potential AE (e.g. bleeding, pain, swelling, infection, periimplantitis) the AE case report form in the database needs to be completed in a timely manner. Moreover, **device deficiencies with SADE potential** (e.g. nerve encroachment, sinus perforation, etc.) must be recorded in the SAE case report form and follow the expedited reporting requirements (**within 24 hours**).

6.3.4 ADE Reporting

Adverse device effects must be recorded and submitted to RevBio by completing the AE case report form in the EDC system within five working days of awareness of the event. Safety reporting to the Institutional Review Board (IRB) should occur according to the requirements of the local IRB.

Bone loss reporting: Continuous substantial reduction of the peri-implant bone level is a sign of failure of the implant system. The first European Workshop on Periodontology specified an average marginal bone loss of less than 1.5 mm bone loss within the first year after the insertion of the prosthesis, and thereafter less than 0.2mm annual bone loss as criteria for measuring success.⁵⁰ This has been a standard and a basis for success criteria since it was defined in 1993. A more recent systematic review article in 2012 reported 2 mm of bone loss being universally acceptable

at one year.⁵¹ Based on this information and since this is a pilot study, the central radiologist will flag any bone level changes that are greater than 2 mm in the first year post-functional loading. The study manager will review the flagged values and discuss with the principal investigator whether the bone level change will be reported as an ADE.

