3.11.8 Periapical Radiographs

Standardized peri-apical radiographs of the area being treated will be recorded pre-operatively, at surgery after device placement, during implant uncovering, at the prosthetic records visit, at insertion of the definitive restoration, and 3, 6, 12, 18, and 24 months post-functional loading. The radiographs must be of high quality and definition, so as to identify the bone contours in question. Ideally the entire implant should be visible on the radiograph. However, it is not essential that the apical end of the implant is contained within the radiograph; in case it is not, at least three threads from the top of the implant showing first bone-implant contact must be visible in the image. These radiographs will be used for crestal bone level assessment and evaluation of implant success (e.g., presence of encapsulation as determined by a continuous radiolucency around the implant).

Radiographs will be digital, using either a direct sensor system or an indirect system with Photostimulable Phosphor (PSP) plate. The patient-specific, custom stent fabricated during the Qualifying Exam must be used. All settings must be noted and consistently used on subsequent visits. To standardize the series of periapical radiographs, the same customized sensor/phosphor plate holder and beam aiming device will be used throughout the study for each study implant site. The radiographs will be captured with the sensor/phosphor plate placed parallel to the implants and the X-ray beam directed perpendicular to the implants. The digital image should will be saved and the file name will be formatted as follows: Subject number (XX-XX), Subject initials (XXX)_Image date (DD MMM YYYY), i.e., 01- 01_ABC_04 Nov 2019. The files will be uploaded as a DICOM file into the Electronic Data Capture system. The records will contain the kV, mA, and exposure time settings.

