5.1 Schedule of Procedures and Assessments

The schedule of administrative, treatment and evaluation visits will follow the matrix detailed in Table 1. The timing of the scheduled events listed in the table will be acceptable if it is within the tolerances listed. Except for the First Surgical Visit, i.e., the extraction, test device and implant placement visit, it is permissible for portions of the procedures to be completed on separate visits provided they are within the allowable schedule windows. A record of procedure and evaluation dates will be maintained.

Table 1: Schedule of Procedures and Assessments

Visit # Visit Name Visit Window	Visit #	Visit Name	Visit Window
---------------------------------	---------	------------	--------------

Visit 1	Screening	
Visit 2	Qualifying Examination	
Visit 3	First Surgical	< 45 days from screening
Visit 4	Post-Operative Follow-up	2 weeks ± 3 days after implant surgery
Visit 5	Implant Uncovering	13 weeks ± 1 week after implant surgery
Visit 6	Restorative Records	3 weeks ± 1 week post-uncovering
Visit 7	Definitive Restoration (Loading)	4 - 6 months from implant insertion
Visit 8	3-month follow-up	3 months ± 2 weeks post-functional loading
Visit 9	6-month follow-up – Primary Endpoint	6 months ± 1 month post-functional loading
Visit 9.5	9-month follow-up	9 months ± 1 month post-functional loading
Visit 10	12-months follow-up	12 months ± 2 month post-functional loading
Visit 11	15-months follow-up	15 months ± 2 month post-functional loading
Visit 12	18-months follow-up	18 months ± 2 month post-functional loading
Visit 13	21-months follow-up	21 months ± 2 month post-functional loading
Visit 14	24-months follow-up	24 months ± 2 month post-functional loading

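### The central bone-loss flag (more than 2 mm) covers only the first year after loading, while crestal bone films and AE reporting run to 24 months, so bone-loss ADEs are ascertained differently in the two years

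*Combined protocol and SAP*

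**What the plan says.** Section 6.3.4 (ADE Reporting, paragraph on bone loss) sets one central rule: "the central radiologist will flag any bone level changes that are greater than 2 mm in the first year post-functional loading". It then says what follows from a flag: "The study manager will review the flagged values and discuss with the principal investigator whether the bone level change will be reported as an ADE". No other section sets a central trigger for bone level.

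The same paragraph names continuing bone loss as a sign of failure and cites two benchmarks from a workshop consensus: less than 1.5 mm in the first year after the prosthesis, "and thereafter less than 0.2mm annual bone loss as criteria for measuring success". The second benchmark is attached to no flag.

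Section 3.11.8 schedules periapical films "at insertion of the definitive restoration, and 3, 6, 12, 18, and 24 months post-functional loading", and states their purpose: "These radiographs will be used for crestal bone level assessment and evaluation of implant success". Section 3.10 gives the same post-loading schedule. Section 7.2 sends the radiographic data to a single central reader who is blinded to subject and time point, and gives no cut-off date. Section 6.3 keeps AE reporting open until the final visit, and Section 7.3 summarizes all adverse events. Table 1 in Section 5.1 sets Visit 10 at "12 months ± 2 month post-functional loading".

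**The concern.** The flag is the only place where a calibrated, blinded measurement feeds the ADE decision. It stops at one year, but the films and the reporting of adverse events do not. A subject whose cumulative loss first passes 2 mm at 18 or 24 months has no central trigger. Whether that loss becomes an ADE then depends on the investigator noticing and reporting it.

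This matters because the study material is meant to resorb and be replaced by bone over several months (Section 3.2), and the pilot is meant to inform a larger study (Section 3.1). Slow, progressive loss is the pattern that Section 6.3.4 itself warns about. If bone-loss ADEs from the two years are later set side by side, part of any difference could come from how they were found.

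**Working it through.** The plan gives no figure to reproduce here: the sample size of 20 has no calculation behind it (Section 3.5) and no tests are planned (Sections 7.1 and 7.2). The check is a count, some worked paths and a range.

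**1. Coverage of the flag.** Post-loading films: 3, 6, 12, 18 and 24 months (Section 3.11.8). Inside the first year: 3 of 5. Outside: 2 of 5. Follow-up time outside: 24 − 12 = 12 of 24 months, or 50%.

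**2. The Visit 10 window.** 12 ± 2 months is 10 to 14 months. A film at month 13 is on schedule, yet on a literal reading it is not in the first year. The share of the window after month 12 is (14 − 12)/(14 − 10) = 50%. The count in step 1 treats the nominal 12-month film as covered; the text leaves this open.

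**3. Worked paths.** The losses are assumed; the documents give none. The current rule flags if year-1 loss exceeds 2 mm. The extended rule flags if loss from the Visit 7 film exceeds 2 mm at any post-loading film. The last column divides year-2 loss by the cited 0.2 mm per year.

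| Year 1 (mm) | Year 2 (mm) | Total (mm) | Current flag | Extended flag | Year 2 ÷ 0.2 |
|---|---|---|---|---|---|
| 1.2 | 1.2 | 2.4 | no | yes | 6 |
| 1.9 | 0.5 | 2.4 | no | yes | 2.5 |
| 1.5 | 1.0 | 2.5 | no | yes | 5 |
| 0.5 | 2.5 | 3.0 | no | yes | 12.5 |
| 0.5 | 1.2 | 1.7 | no | no | 6 |

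The two cited benchmarks add to 1.5 + 0.2 = 1.7 mm at 24 months.

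**4. How many subjects this could involve.** Let p be the true proportion whose cumulative loss first passes 2 mm in year 2. The documents give no p, so a range is assumed, with all 20 subjects evaluable and independent. Expected number = 20p; chance of at least one = 1 − (1 − p)^20.

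| p | Expected | Chance of at least one |
|---|---|---|
| 5% | 1 | 64% |
| 10% | 2 | 88% |
| 15% | 3 | 96% |
| 20% | 4 | 99% |

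Under the current text the expected number of central flags in year 2 is 0 at every p.

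**5. What investigators might still report.** At p = 10% (2 expected cases), unaided detection of 0%, 50% or 100% gives 0, 1 or 2 reported cases. The documents do not fix that detection rate, so the shortfall cannot be fixed either.

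**The case against.** The strongest reply is that other routes stay open to 24 months. The investigator asks about adverse events and reviews records at every visit (Section 3.11.4). Table 3 lists bone loss around the implant and loss of crestal ridge height as expected ADEs with no time limit. An event judged even possibly device-related counts as an ADE (Section 6.1.3). Section 3.11.1 addresses excessive bone loss without limiting it to year 1. All of this stands. What it does not supply is a calibrated measurement or a threshold: Section 3.11.4 consists of talking to the subject and reading records.

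A reader might go further and infer that year-2 bone loss is never reported, or that the safety tables will show bone-loss ADEs falling in year 2 by construction. The documents do not support either. The investigator route remains. A flag only prompts a discussion and does not itself create an ADE. Section 7.3 plans no breakdown by year.

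The window also has a reason. The device-event endpoint (Section 2.2.1) covers the 12 months after loading, and the crestal bone endpoint (Section 2.2.3) is no more than 2 mm lost at 12 months. The flag matches both, and Section 6.3.4 justifies 2 mm as a one-year figure for a pilot. This stands too.

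Finally, central reading of the 18- and 24-month films is implied rather than stated, because Section 7.2 describes it under secondary endpoints. That is a fair point, and a further reason to say so explicitly.

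**Conclusion.** The concern holds as a gap in safety ascertainment. From month 12 the plan drops from central measurement plus investigator reporting to investigator reporting alone, while films for the same purpose continue. Cumulative loss that first exceeds 2 mm in year 2 has no central trigger, and bone-loss ADEs in the two years are not ascertained alike. Under-reporting in year 2 is likely but not certain, and its size cannot be derived from the documents; the rates and loss paths above are assumptions. No defined primary or secondary endpoint is affected.

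Two details make the rule unclear even within its own window: whether a Visit 10 film after month 12 counts as first year, and who applies a time-limited flag when the reader does not know the time point.

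**What to change.** In Section 6.3.4, apply the existing central flag, at its existing threshold, to every scheduled post-loading periapical film through Visit 14 (3, 6, 12, 18 and 24 months). Include any Visit 10 film taken within its 10 to 14 month window. Define the change as measured from the Visit 7 film, which Section 3.9 calls the baseline image. State that the flag is applied after the blinded readings are decoded, and by whom.

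In Section 7.2, state explicitly that the 18- and 24-month films are centrally read. If bone-loss ADEs are reported by period, state how each period was ascertained.

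The sponsor should also reconcile the rule with the later-year benchmark that the same paragraph cites. The last path in the first table shows why: year-2 loss at six times the cited annual figure still raises no cumulative flag. No new threshold is proposed here.

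Cost: no new imaging. If the later films were not already to be read centrally, the addition is at most 20 × 2 = 40 periapical readings, plus decoding and a few more flag reviews. The safety count may look somewhat less favourable.

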6.3.5 SADE Reporting

In the occurrence of a serious adverse device effect, expedited reporting requirements are followed. The SAE case report form should be completed within 24 hours of awareness of the event in the EDC system. RevBio will receive an automated notification generated by the EDC system.

The product safety officer at RevBio will work with the Investigator to determine whether the event is anticipated (ASADE) or unanticipated (USADE). In case of USADE, the investigator must promptly notify its reviewing IRB as soon as possible, but no later than ten (10) working days after first learning of the event.

Since this is a multi-center study, RevBio will inform investigators at all participating centers of any reported USADEs related to this protocol and the study device. Copies of such external USADE reports should be forwarded to the IRB for review and a copy must be kept in the investigator site files.

6.3.6 Additional Safety Reporting

RevBio will report additional safety information to the centers that is relevant to the protocol or study device and may affect the risk/benefit ratio, the rights, safety or welfare of subjects, or the integrity of the study. Such reports may include notification of any changes to the instructions for use, any publications or interim reports, or any product recalls.

6.4 Monitoring of Subjects with Adverse Events

Any AE that occurs during the course of this study must be monitored and followed-up by the investigator until one or more of the following have occurred:

- The AE is resolved,
- Pathological laboratory findings have returned to normal,
- Steady state has been achieved, or
- It has been shown to be unrelated to the study products.

The outcome of an event will be pursued until resolution or until the last data queries are issued following the subject's last study visit. For screen failure subjects, ongoing AEs, ADEs, and DDs

must be followed and updated until the date the subject is deemed a screen failure. For subjects documented as lost to follow-up, ongoing AEs, ADEs, and DDs will not be followed. It is the responsibility of the sponsor to cooperate with the investigator to assure that any necessary additional therapeutic measures and follow-up procedures are performed.

The Clinical Events Committee (CEC) will be an independent board who will not be participating in the study and will adjudicate SAEs reported in the study.

7 Analysis of Endpoints

7.1 Analysis of Primary Endpoints

The primary endpoint in this pilot study will be summarized descriptively and no hypothesis tests are planned.

7.2 Analysis of Secondary Endpoints

All secondary endpoints will be summarized descriptively, and no hypothesis tests are planned. Secondary endpoints include implant success, dimensional changes of bone around the localized region of the implant as determined from radiographic data (periapical and CBCT), qualitative bone density changes in the localized region of the implant as determined from CBCT data, changes in periodontal health measurements, and subject satisfaction (esthetics, function, and level of pain). The radiographic data will be sent to a centralized location to be evaluated by a single reader using a calibrated measuring tool. The images will be provided to the evaluator individually coded and randomized by a third party to make the identity of the subject and the time point of image capture not identifiable by the evaluator, rendering the evaluator blinded. A central radiologist will assess evidence of encapsulation, bone dimensional changes and density values from the radiographs.

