2.2 Secondary Endpoints

2.2.1 Incidence and Severity of Device Attributed Adverse Effects and Events

The **first secondary endpoint** will be to demonstrate low incidence and severity as well as short duration of adverse device-attributed systemic effects and events as reported by study subjects and/or investigator/monitors throughout the 12-month post-functional loading term.

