3.9 Study Treatment Plan

Subjects enrolled in the study will have had, during the Surgical Visit, a test site which met the criteria of an initially placed implant demonstrating inadequate stability. After implant removal, the TN-SM is applied to the site and the implant is reinserted per the Tetranite IFU – Document # 50001-00 (Appendix 1). Immediate stabilization is assessed by applying a torque of 20 Ncm applied directly to the implant 15 minutes after implantation. This level is a clinically relevant indicator of stability and is expected to be a sub-threshold and nondestructive test.⁴⁸ After successful completion of the torque test, all implants will be closed with a cover screw and soft tissues left to granulate over the socket crests. Monofilament sutures will be used at the discretion of the study site before and after soft tissue adaptation. A standardized periapical image will be captured for documentation of the crestal bone level pre-extraction and after TN-SM device and implant placement.

Two weeks following placement of the TN-SM device and the implant, all subjects will return for evaluation of the study site for healing and possible suture removal. A localized CBCT scan of the region of the study site will be performed and will serve as baseline.

All subjects will return at 13 weeks following the TN-SM device implantation to uncover the implant. At this point, short-term stabilization will be assessed by applying a torque of 35 Ncm to the implant. The test is performed at a clinically relevant torque level to demonstrate readiness for restoration of an implant supported prosthesis.⁴⁹ A healing or standard abutment will be placed during the visit. A standardized periapical image for documentation of crestal bone level and for evaluation of indicators of encapsulation will be captured. Photographic records of the study site will be captured before uncovering surgery and following abutment placement and soft tissue adaptation.

Following a three to four-week healing period, records will be obtained for fabrication of a crown restoration. These records will consist of the following: final impression or scan of the test site dental arch, an impression or scan of the opposing dental arch, a jaw relation record and a shade registration of the dentition. Photographic records will also be captured at this time.

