3.11.4 Adverse Event Check

Following surgery and at each visit until the end of the study, the Investigator will determine if any adverse events occurred since the last study visit by speaking with the subject and reviewing any dental and medical records. These Adverse Events (AEs), along with any adverse events from the current study visit, should be documented and reported as described in Section 6.3 of the protocol. In addition, the Investigator will evaluate the status of any ongoing adverse events throughout the study as specified in Section 6.4.

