3.11.10 Intra-oral Photographs

Standardized intra-oral photographs of the area being treated will be taken throughout the study

for documentation of procedures as well as results. The following standard field of view scales will be used:

- Complete dental arch a view including the entire alveolar ridge and all teeth in the arch
- Segment of the region of interest a view centered on the implant site and including between 12 and 15 mm view of surrounding tissues, the long axis of the image will coincide with the mesio-distal direction.

The following aspects of view will be used:

- Occlusal view a view nearly perpendicular to the occlusal plane, a mirror may be used to capture the image
- Facial view a view nearly perpendicular to the facial surfaces of the teeth in the area of interest, a mirror may be used to capture the image
- Occluso-facial view a view nearly perpendicular to the mesio-distal direction in the area of interest and approximately 45 degrees from the occlusal plane and the facial surface of the teeth
- Occluso-lingual view a view nearly perpendicular to the mesio-distal direction in the area of interest and approximately 45 degrees from the occlusal plane and the lingual surface of the teeth, a mirror may be used to capture the image

Ideally the following clinical photographic images will be captured during the study visits as a matter of routine. Additional images of other significant findings will also be recorded.

Preoperative Baseline, Visits 1, 2, or 3:

- Facial view of the segment
- Occlusal view of the segment
- Occlusal view of the entire dental arch where implant will be placed
- Occlusal view of the entire opposing dental arch

Surgical, Visit 3:

- Occlusal view of the segment after extraction
- Occlusal view of the segment after trial implant placement
- Occlusal view of the segment after definitive implant placement and TN-SM trim
- Facial view of the segment after definitive implant placement and TN-SM trim

• Occlusal view of the segment after closure

Post-Surgical Follow-up, Visit 4:

- Occlusal view of the segment as the patient arrives
- Occlusal view of the segment at end of visit

Implant Uncovering, Visit 5:

- Occlusal view of the segment as the patient arrives
- Occluso-facial view of the segment with torque test hardware in place
- Occluso-buccal view of the segment with the abutment in place at the end of visit

Prosthetic Records, Visit 6:

- Occlusal view of the segment as the patient arrives

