5.3 Surgical Procedure (Visit 3)

This visit should be completed within 45 days of screening. In particular, the subject will have the following procedures and/or evaluations performed and documented at this visit:

- Dental and medical history
- Concomitant medication
- Adverse event check
- Oral hygiene
- Informed consent
- Tooth extraction
- Enrollment Inclusion/Exclusion criteria
- TN-SM device and implant placement
- Implant stability by clockwise torque with maximum at 20 Ncm to confirm stabilization
- Standardized periapical radiographs
- Intra-oral photographs

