5.5 Implant Uncovering (Visit 5)

At 13 weeks (± 1 week) following implant surgery, the implant will be uncovered, the short-term implant stabilization will be checked, a healing or standard abutment will be placed, and the soft tissue adapted around the abutment. Short-term implant stabilization will be tested by applying a clockwise torque of 35 Ncm to the implant. If the implant does not rotate with torque application, stabilization will be considered a success of the device and the event will be logged as a "success of short-term stabilization". Should the implant rotate with torque application, the abutment will be removed, and the implant will be left and allowed to heal for an additional month and re-evaluated for successful integration. Lack of stabilization will be considered a failure of the device and the event will be logged as a "failure of short-term stabilization". In particular, the subject will have the following procedures and/or evaluations performed and documented at this visit:

- Dental and medical history
- Concomitant medication
- Adverse event check
- Oral hygiene evaluation
- Uncover implant, place healing abutment
- Implant stability by clockwise torque with maximum of 35 Ncm to confirm stabilization
- Standardized periapical radiograph
- Intra-oral photographs

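### Migration of TN-SM is a listed device effect, but nobody is told to look for it on the CBCTs already taken, so a low or zero count cannot be read as absence of symptom-free displacement

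*Combined protocol and SAP*

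**What the plan says.** **The effect is anticipated.** Table 3 (Section 6.2.6) has a row for migration of TN-SM among the mechanical complications, rated mild and probable. The table header is broken in the supplied text, so the frequency scale behind that rating cannot be read. Section 4.7.1 warns that TN-SM left in the maxillary sinus could lead to a foreign body reaction, sinusitis or chronic infection.

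**How device effects are found.** Section 2.2.1 counts them "as reported by study subjects and/or investigator/monitors throughout the 12-month post-functional loading term". Under Section 3.11.4 the investigator looks for events at each visit "by speaking with the subject and reviewing any dental and medical records".

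**What the scans are for.** At two weeks (Section 3.9), "A localized CBCT scan of the region of the study site will be performed and will serve as baseline". Section 2.2.4 uses CBCT for bone volume and bone density. Section 7.2 sets the central task: "A central radiologist will assess evidence of encapsulation, bone dimensional changes and density values from the radiographs". Section 6.3.4 has the central radiologist flag bone level changes over 2 mm in the first year after loading for possible reporting as an ADE. No other flag from the central reader to ADE review is stated.

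**What is tabulated.** Section 7.3 reports recorded adverse events as numbers and percentages of subjects.

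**The concern.** TN-SM is injected as a viscous liquid, and more may be added after the implant is reinserted (Sections 4.1.1 and 5.3.4). Sites may be maxillary or posterior, and a dehiscence or fenestration of up to 5 mm is allowed (Synopsis; Section 5.3.3). Some material could end up outside the socket without symptoms. Interview and routine visits are weakest for such cases.

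The first secondary endpoint is meant to demonstrate a low incidence of device-attributed effects, and the pilot is also meant to test measures for a larger study (Sections 2 and 3.1). If few or no migrations are recorded, a reader cannot tell whether no material moved or whether nobody looked. TN-SM is resorbed over several months (Section 3.2), so an early look that is missed may not be recoverable from later scans.

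**Working it through.** **1. Plan's own figure.** There is none to reproduce. The 20 subjects are a fixed cap (2 centers × 10, Section 3.5), with no rate, power or interval behind it.

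**2. Who would see displaced material, and is anyone told to look?**

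| Opportunity | Source | Instruction to look for TN-SM outside the socket? |
|---|---|---|
| Surgery and photographs ("Occlusal view of the segment after definitive implant placement and TN-SM trim") | 3.11.10 | No |
| Two-week visit and localized CBCT | 3.9, 5.4 | No |
| 13 weeks ("the implant will be uncovered, the short-term implant stabilization will be checked") | 5.5 | No |
| Record review, which can include radiographs as source documents | 3.11.4, 9.2.3 | No |
| Central read | 7.2 | No: encapsulation, bone dimensions, density |
| Flag from central reader to ADE review | 6.3.4 | No: bone level change over 2 mm |

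The opportunities are real, but none is a directed search with a recorded number of subjects examined.

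**3. Scans available.** Post-placement CBCTs are scheduled at 2 weeks, at loading, and at 3, 6, 12 and 24 months: 6 × 20 = 120. Section 3.11.9 also lists 18 months, which would make 7 × 20 = 140. The two-week scan matters most: 1 × 20 = 20, if all attend Visit 4. The required field is the site plus 12 to 15 mm.

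**4. What a directed read would support.** With complete detection, the exact two-sided 95% upper limit for 0 of k is 1 − 0.025^(1/k). The values of k below 20 are an assumed range for scans that cannot be assessed.

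| k assessable | Upper limit for 0 of k |
|---|---|
| 20 | 16.8% |
| 19 | 17.6% |
| 18 | 18.5% |
| 17 | 19.5% |

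For 1 of 20 the exact interval is 0.1% to 24.9%.

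**5. What a zero count means when detection is unknown.** Let p be the true rate of displacement and s the chance that a case is noticed and recorded. Both are assumptions; the documents give neither. The chance of zero recorded in 20 is (1 − p·s)^20, and the upper limit on p is 16.8% / s, capped at 100%.

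| s | Chance of 0 of 20 if p = 10% | Upper limit on p from 0 of 20 |
|---|---|---|
| 1 | 12% | 16.8% |
| 0.5 | 36% | 33.7% |
| 0.25 | 60% | 67.4% |
| 0.1 | 82% | 100% (uninformative) |

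This is an illustration, not an estimate of under-reporting. It shows only that the same zero can mean very different things.

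**The case against.** **Ascertainment is not limited to complaints, and a denominator exists.** A reader might infer that migration can surface only if a subject or investigator volunteers it, and that any count has no denominator. The documents do not support that. Section 2.2.1 also names monitors, record review can include the CBCTs, and sites see the area at surgery, at two weeks and at uncovering. The treated subjects are a known denominator for reported events. What stands is narrower: the number examined for silent displacement is unknown.

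**Serious cases already have a route.** A reader might infer from the sinus warning that dangerous displacement would go unreported. Section 6.3.3 requires device deficiencies with potential for a serious device effect, such as sinus perforation or nerve encroachment, to be reported within 24 hours. Table 3 lists oro-sinus intrusion or fistula separately, as severe. These routes work once something is noticed; they do not make anyone look.

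**The endpoint wording is narrower.** Section 2.2.1 speaks of systemic effects and events, so silent local material is arguably outside it. The Synopsis states the same endpoint as device-related adverse events without that limit. The objection weakens the link to the endpoint but does not remove it.

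**The instruction may sit elsewhere, and the read may fail.** The text of the IFU, the case report forms and the hazards analysis are not supplied, so the point is limited to the text at hand. The documents also do not say whether TN-SM can be told apart from bone on CBCT. Both cautions stand. The second is met by a not assessable category.

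**The plan is descriptive and many effects are found clinically.** True. That bears on priority. Migration differs in being specific to this device and in possibly being visible on scans already scheduled.

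**Conclusion.** The point holds in limited form. Migration of TN-SM is a named expected effect that the supplied text ascertains only passively, although suitable scans are already taken and centrally read for other purposes. A low or zero count in the safety tables would be a count of noticed and reported cases. It would not be evidence that symptom-free displacement was absent.

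The documents do not allow the under-reporting to be sized. The 16.8% limit for 0 of 20 describes what a complete directed read could support, and assumes that all 20 two-week scans are assessable and that visible material is always detected. Material beyond the 12 to 15 mm field would still be missed.

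A reader might go further and infer that the safety endpoint is invalid or the primary endpoint affected. Nothing supports that: the primary composite does not depend on TN-SM position, and reported events are still counted properly. This is a cheap improvement of low to moderate priority.

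**What to change.** **Section 7.2.** Add one item to the central read of each post-placement CBCT: radiopaque material consistent with TN-SM outside the socket or osteotomy (sinus or nasal cavity, inferior alveolar canal, adjacent soft tissue): yes / no / not assessable. Read the scans in the normal coded and randomized order. Pulling the two-week scans forward as a batch would disclose the time point that Section 7.2 hides.

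**Visit 4.** For timely safety action, have the investigator record the same item from the two-week CBCT already taken.

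**Forwarding.** The third party holding the codes sends any central yes to the investigator for assessment under Section 6.2. Label it material outside the socket, not migration: Visit 3 has "Standardized periapical radiographs" but no CBCT, so overfill at placement cannot be excluded from the scan alone. The Visit 3 films and the photographs after trimming can help the investigator judge.

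**Section 7.3.** Report subjects with the finding over subjects with an assessable two-week scan, and list findings seen only on later scans separately. An exact interval is optional. If TN-SM cannot be told apart on CBCT, report that displacement was not assessable by imaging, not zero.

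**Cost.** One or two form items, one forwarding step and one table. No new scan, visit, reader or subject is needed. The downsides are some incidental findings or overfill to assess and a possibly higher ADE count.
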